# 10.2. Analysis Sets

For purposes of analysis, the following analysis sets are defined:

Analysis Set	Description
Enrolled Set	All patients who sign the informed consent form
Safety Analysis Set (SAS)	All patients assigned to study treatment and who received
	≥1 dose of study treatment (IFX-1 for monotherapy arm,
	IFX-1 or pembrolizumab for combination arm)
Full Analysis Set (FAS)	All patients assigned to study treatment
Per Protocol Set (PPS)	All patients who received ≥1 dose of study treatment and
	who have ≥1 post-baseline tumor assessment

Protocol violations will be reviewed in the data review meeting. The decisions will be documented in the meeting minutes and finalized before database lock.

In general, safety analyses will be based on the SAS. The primary efficacy analyses will follow an intention-to-treat concept and will be performed on the FAS.

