## 10.3.1. Efficacy Analyses

All efficacy analyses will be performed on the FAS. All analyses will be conducted separately by treatment arm. The 2 treatment arms will be compared descriptively. Patients will be analyzed descriptively and stratified by locally advanced or metastatic cSCC.

The primary efficacy variable is the best ORR (investigator assessed) based on modified RECIST v1.1 criteria (Eisenhauer et al., 2009) and iRECIST criteria (Seymore et al., 2017). The number and percentage of responders will be displayed per treatment arm along with its 95% confidence interval according to Clopper-Pearson.

Patients who discontinue the study after assignment to treatment due to 1 of the following reasons will be counted as non-responder if they have not shown response before discontinuation:

- Lack of efficacy
- AE at least possibly related to study treatment
- PD/iCPD
- Clinical deterioration

Statistical inference will be based on the thresholds defined by the Simon's 2-stage design. For decision criteria at the interim analysis, please refer to Section 10.3.4. At the final analysis, the null hypothesis of an ORR of  $\leq$ 5% will be rejected if >3 patients out of a total of 29 patients respond (CR/iCR/PR/iPR). Due to dropouts, the number of patients evaluable for the primary endpoint might not be exactly 29. In this case, appropriate statistical methods will be applied to correct for the deviation from the planned sample size of 29 evaluable patients (Koyama and Chen, 2008). In this case, appropriate statistical methods will be applied to correct for the deviation from the planned sample size of 29 evaluable patients (Koyama and Chen, 2008). Further details will be specified in the SAP.

Additionally, the number and percentage of patients per RECIST tumor response category will be displayed for each scheduled tumor assessment time point.

Secondary Endpoint	Statistical Analysis Methods

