Response (CR/iCR/PR/iPR) duration	Duration of response will be analyzed for patients who reach at least PR/iPR at any time during the study using Kaplan-Meier methods. A responding patient who experiences any form of progression will be evaluated as a patient with event. The starting point is the first diagnosis of CR/iCR or PR/iPR. The time point of the event will be the diagnosis of progression according to RECIST. Responding patients without progression will be censored at their last tumor assessment showing response. Patients who never responded will be excluded from this analysis.
SD duration	Duration of SD will be analyzed using Kaplan-Meier methods. The starting point is the first study treatment administration. A patient who experiences any form of progression will be evaluated as a patient with event. The time point of the event will be the diagnosis of progression according to RECIST (PD) or iRECIST (iCPD). Patients without progression will be censored at their last tumor assessment showing response or any other best overall response except PD/iCPD.
PFS	PFS will be analyzed using Kaplan-Meier methods. A patient who experiences any form of progression or who

	dies of any cause will be evaluated as a patient with event.		
	The time point of the event will be the diagnosis of the		
	first progression according to RECIST/iRECIST or the		
	date of death. Patients without progression and still alive		
	will be censored at their last tumor assessment.		
OS	OS will be analyzed using Kaplan-Meier methods. Death		
	by any cause will be evaluated as event. Patients who are		
	still alive when they discontinue the study will be		
	censored at their last recorded date of being alive.		
Disease control rate	The number and percentage of patients with		
	SD/confirmed SD (iSD) per modified RECIST		
	v1.1/iRECIST or PR/iPR or CR/iCR will be displayed		
	per tumor assessment timepoint.		

Exploratory endpoints will be analyzed descriptively. Further details will be provided in the SAP.

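### As written, SD duration is not limited to patients with stable disease, so unless the SAP restricts it, it estimates time to progression in all treated patients

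*Combined protocol and SAP*

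**What the plan says.** The secondary endpoint table in Section 10.3.1 treats neighbouring endpoints differently.

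- **Response duration** is limited to patients reaching at least PR/iPR. The row spells the exclusion out, "Patients who never responded will be excluded from this analysis", so its analysis set is plain.
- **SD duration**, the next row, opens with the method and the start of the clock: "Duration of SD will be analyzed using Kaplan-Meier methods. The starting point is the first study treatment administration". Any form of progression is an event, dated at PD under RECIST or iCPD under iRECIST. Patients without progression are censored at their last tumor assessment "showing response or any other best overall response except PD/iCPD". The row names no subset and does not mention death.
- **PFS** counts progression or death from any cause and dates progression at its first diagnosis.
- **Disease control rate** (CR/iCR, PR/iPR or SD) is displayed as a count and percentage "per tumor assessment timepoint".

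The default population stands at the head of the section: "All efficacy analyses will be performed on the FAS". Section 10.2 defines that set as "All patients assigned to study treatment".

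Section 8.2.2 defines best overall response. The RECIST response table in Appendix 3 asks for SD to be documented at least once more than 4 weeks from baseline. Section 10.3 leaves exact endpoint definitions to the SAP and calls the protocol text a summary.

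**The concern.** Where a subset was intended, in the response-duration row, it was written out. The next row has no such sentence, so the full analysis set applies. A patient whose first scan shows progression then contributes an SD-duration event at about week 7 without ever having had stable disease, and responders stay in the risk set.

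A reader would take the Kaplan-Meier median under this label as the time for which stable disease holds. With a design built on response rates of 5% and 20% (Section 10.1), most patients are expected not to respond. The SD endpoints will therefore carry much of the remaining description of activity, and Section 10.3.1 plans a descriptive comparison of the two arms.

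**Working it through.** **No planned figure to reproduce.** The documents give no number for SD duration or disease control. The Section 10.1 design figures concern response rate only. The exact two-stage binomial calculation returns early stopping 59.9%, expected size 17.6, Type I error 4.7% and Type II error 19.9%, matching the plan. Nothing below touches them.

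**Who is in the SD-duration analysis, by the text**
1. Population: the full analysis set by default, with no restriction in the row. Patients never dosed have no start date, so in practice this means all treated patients.
2. Event: any progression, which includes progression at the first scan.
3. Censoring: the rule covers patients whose assessment shows response, so responders are included.
4. Compared with PFS, the row lacks death as an event. It also names iCPD where PFS uses first progression. Appendix 4 schedules confirmation imaging 4 to 8 weeks after an unconfirmed progression, so event dates can differ.

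**Size, by illustration.** From the documents: Cycle 1 lasts 7 weeks, later cycles 6 weeks, and assessments fall on Day 1 of each cycle from Cycle 2, that is at weeks 7, 13, 19, 25 and so on. Everything else is assumed:
- a share e progresses at week 7;
- a share s has best response SD, with median time to progression 20 weeks from first dose (13 weeks after week 7);
- a share r = 10% responds, with median 40 weeks after week 7;
- there are no deaths or dropouts.

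For t ≥ 7, the proportion of all patients free of progression is

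S(t) = s × 2^(−(t−7)/13) + r × 2^(−(t−7)/40),

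and the median solves S(t) = 0.5. For e = 40%, at t = 10.9: 0.5 × 0.813 + 0.1 × 0.935 = 0.407 + 0.093 = 0.50.

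| e | s | All-patient median (weeks) | Same, if responders never progress | First scan with S ≤ 0.5 |
|---|---|---|---|---|
| 50% | 40% | 7.0 | 7.0 | 7 |
| 40% | 50% | 10.9 | 11.2 | 13 |
| 30% | 60% | 14.1 | 14.6 | 19 |
| 20% | 70% | 16.8 | 17.5 | 19 |

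The comparison value in SD patients is 20 weeks, which is an input and not a result. On the scan schedule it would be seen at week 25, since 2^(−12/13) = 0.53 at week 19 and 2^(−18/13) = 0.38 at week 25. The 7.0 in the first line follows directly from assuming that half the patients progress at week 7.

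**Second set of assumptions.** SD median 12 weeks and responder median 40 weeks after week 7, with response/SD shares of 5/25, 5/40, 20/25 and 20/40%. Early progression is then 70, 55, 55 and 40%. Since S(7) = 0.30, 0.45, 0.45 and 0.60, the all-patient median is week 7 in the first three. In the fourth S(13) = 0.46, so it is week 13. In SD patients alone the median is 7 + 12 = 19 weeks. That value falls on a scan date, so a simulation of 400,000 patients returns week 19 or week 25.

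**Disease control under the second set.** From best overall response the rate is 30, 45, 45 and 60%. Per visit with all patients in the denominator, it runs from 30–60% at week 7 to 17–36% at week 19 and 10–23% at week 31. With only patients still being assessed in the denominator, it is 73–79% at week 13. The row gives no denominator rule. A single rate can carry an exact interval: 13/29 = 44.8%, Clopper-Pearson 95% interval 26.4% to 64.3%.

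**The case against.** **The section is a summary and exact definitions are left to the SAP.** This stands. No SAP text is in the file, and it may restrict the set. A reader might infer that the plan openly declares an all-patient analysis. It does not: that population is read from the default set, the missing restriction and the censoring rule, and the censoring clause fixes a date and does not define who is analysed. Still, the text as it stands leads there, and the contrast with the response-duration row makes it more than missing detail.

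**It is not a copy of PFS.** Correct. Death is not an event, and iCPD may be dated later than first progression.

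**The illustration depends on an unknown share.** Correct. With 20% progressing early, the medians are about 17 and 20 weeks. The documents do not support saying that the median is always driven by the first scan.

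**Starting the clock at first dose is not an error.** Agreed. The difficulty is who is included.

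**The per-visit disease control table contradicts nothing.** A reader might infer that the listed endpoint must be one rate based on best response. The endpoint lists do not say so, whereas the primary endpoint does specify best response. A single rate is therefore an improvement and not the repair of an error. It could already be derived from the individual data to be listed.

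**Conclusion.** The point holds for SD duration. Taken as written, and unless the SAP restricts it, the analysis gives time to progression in all treated patients under another name. The gap from the duration in SD patients is large if 40 to 50% progress at the first scan (about 7 to 13 weeks against about 20) and small if about 20% do (about 17 against 20). All shares and the 20-week value are assumptions.

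The weight is low. These are descriptive secondary endpoints, PFS and per-visit response categories are reported beside them, and the response-rate test, its thresholds and the stage decisions do not change.

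**What to change.** - Restrict SD duration to patients with best overall response SD/iSD, using the more-than-4-weeks rule in Appendix 3. Alternatively, keep all treated patients and rename the endpoint time to progression.
- In either case, state how deaths without progression are handled.
- As a free improvement, report one disease control rate per arm from best overall response on the full analysis set, with a Clopper-Pearson interval. Keep the per-visit table as supportive and state its denominator.

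The cost is SAP wording. Restricting to SD patients has two downsides. The set is smaller, so the interval is wider. The subset is also defined after baseline, so its members are progression-free to the first scan by construction, and the result should be presented as descriptive only. Renaming avoids both but leaves the duration of stable disease unestimated.

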## 10.3.2. Safety Analyses

All safety analyses will be performed on the SAS.

An AE is considered as treatment emergent if it starts during or after first administration of study treatment (IFX-1 or pembrolizumab). The number and percentage of patients with TEAEs, SAEs, and AESIs for IFX-1 and/or pembrolizumab will be analyzed, as well as the number of TEAEs, SAEs, and AESIs with the respective MedDRA System Organ Class and Preferred Term. Where AEs are grouped by NCI CTCAE grade or relationship, the maximum grade/relationship per patient and class of AE will be considered. The described analyses will be performed for the treatment period and the follow-up period separately. AEs reported during screening or before first study treatment administration will be categorized as pre-treatment AEs.

Safety laboratory, vital signs, and 12-lead ECG parameters will be analyzed by summary statistics (e.g., number of observations, mean, standard deviation, minimum, median, maximum, lower quartile, upper quartile) for absolute values and changes from baseline by visit. Shift tables comparing baseline and the worst post-baseline assessment will be prepared if applicable.

Categorical safety parameters, like findings from physical examination, will be summarized by absolute and relative frequencies by time point.

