Complement:  C3a (C1D1 only) C5a		Х			х	Х	х	C2,3, 5, then every other cycle		х	First FU		
ADAs for IFX-1 (mandatory) 		х				х	х	C2, 3, 5, then every other cycle		х	First FU		
Pharmacokinetics (mandatory) 		х	X		х	X	D22 pre- & post- dose D36 pre- dose only	C2, 3, 5, then every other cycle		х	First FU		
Skin cancer biopsy (or metastasis biopsy)  Mandatory	х							Only Stage 2 patients					
Optional				×		15		Only Stage 2 patients only at CR/iCR/PR/iPR and/or PD					

- (1) Screening: ≤4 weeks prior to the first administration of IFX-1.
- (2) End of treatment (EOT) Visit to be performed 30 days after the last IFX-1 or pembrolizumab administration or before the patient starts on another antineoplastic therapy, whichever occurs earlier.
- (3) Locally advanced cSCC patient to provide archived or newly obtained tumor material for central pathology review for confirmation of diagnosis of cSCC.
- (4) Disease/Response assessment according to modified response evaluation criteria in solid tumors (RECIST) version 1.1/RECIST for immune related therapeutics (iRECIST) (magnetic resonance imaging, computed tomography (CT), or CT scan with contrast, of chest, abdomen, pelvis (and other regions where metastases are suspected). Standardized medical photography of ≥1 index skin tumor must be added. Re-assessments must be made with the same imaging technique as used at baseline. Imaging will also be performed at time of complete response (CR) confirmation. Response assessments to be performed ±7 days. In case patients experience a partial response (PR)/confirmed PR (iPR) or CR/confirmed CR (iCR) that lasts ≥1 year, imaging frequency can be decreased to every other cycle.
- (5) IFX-1 administration by intravenous route as 30-minute (-5/+10 minutes) infusion, followed by at least 60 minutes of observation. Start of administration should be seen as "H0".
- (6) Pembrolizumab administration ends 60 minutes (±10 minutes) before IFX-1 infusion start. Pembrolizumab by intravenous route as 30-minute (-5/+10 minutes) infusion, followed by at least 60 minutes of observation.
- (7) Vital signs: heart rate, blood pressure (diastolic and systolic), body temperature, and respiratory rate to be performed at each visit, at pre-dose, and H0+1h (±5 minutes) on the days of administration and whenever medically indicated

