# Phase II portion

The co-primary endpoints of the Phase II portion of Arm B are investigator assessed best ORR for IFX-1 + pembrolizumab, with response being defined as best response of CR/confirmed CR (iCR) or PR/confirmed PR (iPR) per modified RECIST v1.1/iRECIST and frequency, severity, and investigational new drug (IND) attribution of TEAE and serious adverse event (SAE) according

to the Medical Dictionary for Regulatory Activities (MedDRA) coding (version valid at time of reporting) and the NCI CTCAE grading system v5.0.

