# 4.2.2. Secondary Endpoints

# 4.2.2.1. Monotherapy Arm A

Secondary endpoints comprise the following:

- Response (CR/iCR/PR/iPR) and stable disease (SD) duration
- Disease control rate (CR/iCR+PR/iPR+SD)
- PFS
- OS
- Frequency, severity, and IND attribution of treatment-emergent AEs (TEAEs) and SAEs according to MedDRA coding (version valid at time of reporting) and the National Cancer Institute common terminology criteria for AEs (NCI CTCAE) grading system (version 5.0, 27 November 2017)
- Post infusion ( $C_{max}$ ) and trough concentration ( $C_{trough}$ ) of IFX-1
- Development of human ADAs against IFX-1
- Changes in QoL as per the European Organisation for Research and Treatment of Cancer (EORTC)-QoL questionnaire (QLQ)-C30 total score

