#### 9.1.1. Non-serious Adverse Events

- All non-serious AEs must be reported from patient's informed consent until 30 days following discontinuation of study treatment
- All AEs must be followed until the outcome of the event is "recovering" (for stabilization of chronic conditions), or recovered (/with sequelae), and until all queries related to these AEs have been resolved.
- Ongoing AEs should be reviewed at each visit until EOT Visit or study discontinuation. If resolved, the details should be recorded in the eCRF.
- All ongoing AEs at the EOT Visit will have to be followed up until the outcome of the event is "recovering" (for chronic conditions), or recovered, until the EOS visit and until all queries related to these AEs have been resolved.
- If during an AE period, changes for the worse, in frequency of episodes/symptoms or in severity are observed, the final AE entry/report must include the maximum severity and frequency observed for this AE.
- If the patient dies from an event, ongoing AEs can be closed with an outcome "not known" if the outcome was not re-assessed at the day of death.

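### A TEAE is defined by start date alone, so an AE opened in screening that worsens on treatment is tabulated as pre-treatment and is missing from the TEAE endpoint

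*Combined protocol and SAP*

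**What the plan says.** Section 10.3.2 gives the TEAE rule: "An AE is considered as treatment emergent if it starts during or after first administration of study treatment". It adds: "AEs reported during screening or before first study treatment administration will be categorized as pre-treatment AEs". Neither sentence mentions an event that is present before first dose and worsens afterwards.

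Section 9.1.1 says that non-serious AEs "must be reported from patient's informed consent until 30 days following discontinuation of study treatment". The Schedule of Assessments (Section 2, footnote 1) sets the pre-dose window: "Screening: ≤4 weeks prior to the first administration of IFX-1". If an AE gets worse while it is open, Section 9.1.1 requires that "the final AE entry/report must include the maximum severity and frequency observed for this AE".

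Section 9 lists the contents of an AE record. These include severity, seriousness, relationship, and start and stop dates and times. A date of grade change is not listed.

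The endpoint is stated twice. For the Phase II portion of Arm B (Section 4.2.1.2) the safety co-primary is "frequency, severity, and investigational new drug (IND) attribution of TEAE and serious adverse event (SAE) according" to MedDRA coding and CTCAE v5.0 grading. For Arm A (Section 4.2.2.1) the secondary endpoint is "Frequency, severity, and IND attribution of treatment-emergent AEs (TEAEs) and SAEs according to MedDRA coding" and CTCAE grading.

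Appendix 6 counts an exacerbation of a chronic or intermittent pre-existing condition as an AE. Section 8.1.3 treats ongoing diseases diagnosed before enrollment as concomitant diseases, separate from AEs.

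**The concern.** The collection rule and the analysis rule do not fit together. Collection opens AE records up to four weeks before treatment and lets one record run on into treatment. The analysis then sorts records by start date alone. An event that was mild in screening and becomes severe on study drug is a treatment-period change, which a TEAE table is meant to show, yet it goes to the pre-treatment class.

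It also makes the tables inconsistent. If a condition known before consent worsens on treatment, Appendix 6 makes the worsening an AE, and that AE starts after first dose, so it is a TEAE. The same worsening of an event that began between consent and first dose is not.

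At stake is the completeness of a co-primary safety endpoint in Arm B and a secondary one in Arm A. Infection shows how a case could arise. Section 3.3 names infections as an important potential risk of IFX-1, and exclusion criterion 11 bars only known active infections of Grade 3 or higher, so a milder one may be open at first dose.

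**Working it through.** No stated design figure bears on this point. Sample size, type I error and power do not depend on the TEAE rule. The check is a reading of the rules in sequence, followed by simple proportions.

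**Following one event through the rules**

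1. A patient consents and, within the four-week screening window, develops a Grade 1 event. It is recorded, because collection starts at consent (Section 9.1.1).
2. First dose is given with the event ongoing.
3. On treatment the event rises to Grade 3. Section 9.1.1 has the final entry carry the maximum severity and does not call for a second entry. Section 9 gives a record one start date and no date of grade change. The record now shows a pre-dose start and Grade 3. That the updated entry keeps its original start date is an inference, since Section 9.1.1 does not mention the start date.
4. Section 10.3.2 tests the start date. It precedes first dose, so the record is a pre-treatment AE of Grade 3.
5. The event contributes nothing to TEAE frequency, maximum TEAE grade or TEAE attribution.

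**What still catches the event**

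| Type of worsening | Backstop in the plan |
|---|---|
| Becomes serious | SAE counts; Section 10.3.2 does not limit them to treatment-emergent events |
| Laboratory, vital-sign or ECG finding | Shift tables of baseline against worst post-baseline value, prepared if applicable |
| Other event, worse but not serious | None in the summary tables; individual listings only |

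The clear loss is the last row.

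**Size per affected patient**

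Section 10.3.2 uses the maximum grade per patient and class of AE. A patient with another event that qualifies for the same table row therefore loses nothing at patient level. For a patient without one:

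- 29 patients (Phase II size per arm, Section 10.1): 1/29 = 3.4 percentage points.
- 41 patients (upper limit for Arm B including the run-in, Section 10.1: 18 + 23 = 41): 1/41 = 2.4 percentage points. The safety analysis set in Section 10.2 is all treated patients, so run-in patients can be in the denominator.

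**How many patients (assumption, not from the documents)**

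Let s be the share of patients with an AE open at first dose and w the share of those whose AE rises to Grade 3 or higher on treatment. Expected number in 29 patients = 29 × s × w. Chance of at least one = 1 − (1 − s × w)^29.

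| s | w | Expected of 29 | Chance of at least one |
|---|---|---|---|
| 10% | 5% | 29 × 0.005 = 0.15 | 14% |
| 30% | 10% | 29 × 0.03 = 0.87 | 59% |
| 50% | 20% | 29 × 0.10 = 2.9 | 95% |

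These are ceilings for the loss. They include events that also become serious and patients who have another qualifying TEAE.

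**The case against.** **The single-record reading is partly inferred.** Section 9.1.1 does not forbid a new record, and a site could read Appendix 6 as allowing a new AE dated at the worsening. That reading is possible, but Appendix 6 speaks of pre-existing chronic or intermittent conditions and does not tell sites to open a second record for an AE already on file. At best the two texts are unreconciled and sites may record the same case differently.

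**Details are left to other documents.** Section 10.3 defers exact definitions to a separate SAP, and Section 9 defers AE entry instructions to the eCRF guidelines. Neither is among the documents supplied, and either could add a worsening rule. A SAP clause alone would not be enough, however. If a record holds only the start date and the maximum grade, the analyst cannot tell whether that grade was reached before or after first dose.

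**Most severe cases surface elsewhere.** This stands in large part. Grade 4 is life-threatening and will generally meet the seriousness criteria. Hospitalization makes an event serious, and potential drug-induced liver injury is handled as an SAE. A reader might infer that Grade 3 or 4 worsening disappears from safety reporting. The documents do not support that.

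**The biopsy example.** A reader might also infer that every patient is exposed to a pre-dose biopsy infection that would then go uncounted. Inclusion criterion 5 waives the biopsy where no suitable lesion exists, and no infection rate is given. The IFX-1 AESI list is not legible in the public text, so it cannot be seen whether infections have their own table.

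**No decision turns on it.** This also stands. TEAE analysis is descriptive. Section 7.2.2.2.3 uses the word TEAE when sending events for DLT review, but the DLT definition refers to a toxicity that occurs in the assessment period, and Section 5.3.2 gives the steering committee all available safety data. The documents do not support a claim that escalation decisions would be affected.

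**Conclusion.** The point holds in a limited form. As written, Sections 9.1.1 and 10.3.2 together place an AE that opens in screening and worsens in grade on treatment among pre-treatment AEs at its maximum grade, and so outside the TEAE endpoint in both arms. The clear loss is confined to worsening that is not serious and does not appear in shift tables.

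The size is 3.4 percentage points per affected patient in a set of 29, or about 2.4 in a set of 41, and only where that patient has no other qualifying TEAE. The effect on the overall any-TEAE rate may therefore be small. Rates of Grade 3 or higher events and of individual preferred terms are more exposed. A patient-level rate can be lowered or left unchanged, so it would be wrong to infer that every such event lowers it.

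The conclusion assumes that an updated entry keeps its original start date, and that the separate SAP and eCRF guidelines add no worsening rule. How often such events occur is unknown. No efficacy conclusion or design figure is affected, but the plan should be corrected because a co-primary endpoint is involved and the change is cheap.

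**What to change.** Two linked changes are needed.

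1. **Section 10.3.2 and the SAP.** Define a TEAE as an AE that starts, or worsens in CTCAE grade, during or after first administration of study treatment. Amend the pre-treatment sentence so that it covers only events with onset before first dose that do not worsen in grade afterwards.
2. **Section 9.1.1 and the eCRF guidelines.** Require that an AE ongoing at first dose which later worsens is re-entered with the date, grade, seriousness and relationship of the worsening. State how this fits with the Appendix 6 wording on exacerbation.

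The second change should be in place before data are collected, because dates of grade change may not be recoverable later. The cost is a sentence or two in each place, a few more AE records and a slightly higher reported TEAE rate. Sample size and the efficacy analysis are unchanged.
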